11.4.5.2. Other Safety

Vital Signs

Vital signs (temperature, pulse, blood pressure, and respiration rate) will be summarized by baseline and change from baseline to each scheduled assessment time with descriptive statistics. The number and percentage of patients with a treatment-emergent potentially clinically significant value (PCSV) will be summarized for each vital sign variable. The criteria for treatment emergent PCSV will be defined in the SAP.

Laboratory Tests

Laboratory test results will be summarized by baseline and change from baseline to each scheduled assessment time with descriptive statistics.

Number and percentage of patients with a PCSV at any post-randomization time point will be summarized for each clinical laboratory test for all patients and separately for patients in whom the PCSV criterion was normal or missing at baseline.

The number and percentage of patients with a treatment-emergent PCSV will be summarized for each clinical laboratory test. The criteria for treatment-emergent PCSVs will be defined in the SAP.

Shift tables based on baseline normal/abnormal and other tabular and graphical methods may be used to present the results for laboratory tests of interest.

Listings will be provided with flags indicating the out of laboratory range values.

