5.8.2. Clinical Laboratory Measurements

Laboratory measurements include clinical chemistry, hematology, and urinalysis results, and will be converted to values in standard international units. Summaries of laboratory variables will include:

- Descriptive statistics of laboratory result and change from baseline by visit, if applicable.
- The number (n) and percentage (%) of subjects with treatment-emergent PCSVs. This summary will be provided based on all patients in the SAF as well as in the subgroup of SAF patients who did not meet the PCSV criterion at baseline (normal or missing).
- Shift tables based on baseline normal/abnormal will be presented

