6.1.2. PCSV

Patients who had post-baseline PCSV, but missing baseline value will be regarded as having treatment emergent PCSV. Refer to [Appendix](#) for PCSV table.

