eGFR (mL/min/1.73m ²) (Estimate of GFR based on an MDRD equation)	<15 (end stage renal disease) ≥15 - <30 (severe decrease in GFR) ≥30 - < 60 (moderate decrease in GFR) ≥60 - <90 (mild decrease in GFR) ≥ 90 (normal GFR)	FDA draft Guidance 2010 Pharmacokinetics in patients with impaired renal function-study design, data analysis, and impact on dosing and labeling
Creatinine	≥150 µmol/L (Adults) ≥30% change from baseline ≥100% change from baseline	Benichou C., 1994.
Uric Acid		Harrison- Principles of internal Medicine 17 th Ed., 2008.
Hyperuricemia	>408 µmol/L	
Hypouricemia	<120 µmol/L	
Blood Urea Nitrogen	≥17 mmol/L	
Chloride	<80 mmol/L ≥115 mmol/L	

Regeneron Pharmaceuticals, Inc.

Protocol Number R668-AS-1903

Statistical Analysis Plan v1.0

CRITERIA for POTENTIALLY CLINICALLY SIGNIFICANT VALUES (PCSV)

Parameter	PCSV	Comments
Sodium	≤ 129 mmol/L ≥ 160 mmol/L	
Potassium	<3 mmol/L ≥ 5.5 mmol/L	FDA Feb 2005.
Total Cholesterol	≥ 7.74 mmol/L	Threshold for therapeutic intervention.
Triglycerides	≥ 4.6 mmol/L	Threshold for therapeutic intervention.
Lipasemia	≥ 3 ULN	
Amylasemia	≥ 3 ULN	
Glucose		
Hypoglycaemia	≤ 3.9 mmol/L and $<LLN$	ADA May 2005.
Hyperglycaemia	≥ 11.1 mmol/L (unfasted); ≥ 7 mmol/L (fasted)	ADA Jan 2008.
HbA1c	$>8\%$	
Albumin	≤ 25 g/L	
CRP	>2 ULN or >10 mg/L (if ULN not provided)	FDA Sept 2005.
Hematology		
WBC	<3.0 Giga/L (Non-Black); <2.0 Giga/L (Black) ≥ 16.0 Giga/L	Increase in WBC: not relevant. To be interpreted only if no differential count available.
Lymphocytes	>4.0 Giga/L	
Neutrophils	<1.5 Giga/L (Non-Black); <1.0 Giga/L (Black)	International Consensus meeting on drug-induced blood cytopenias, 1991. FDA criteria.
Monocytes	>0.7 Giga/L	
Basophils	>0.1 Giga/L	
Eosinophils	>0.5 Giga/L or $>ULN$ (if $ULN \geq 0.5$ Giga/L)	Harrison- Principles of internal Medicine 17 th Ed., 2008.

Regeneron Pharmaceuticals, Inc.**Protocol Number R668-AS-1903****Statistical Analysis Plan v1.0****CRITERIA for POTENTIALLY CLINICALLY SIGNIFICANT VALUES (PCSV)**

Parameter	PCSV	Comments

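### SAP 10.1 puts every possible CLcr and eGFR value, including normal function, in the PCSV column, which contradicts SAP 5.8.2

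*SAP*

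**What the plan says.** Protocol 11.4.5.2 plans a count of laboratory PCSVs after randomization: "Number and percentage of patients with a PCSV at any post-randomization time point will be summarized for each clinical laboratory test". It leaves the treatment-emergent rule to the other document: "The criteria for treatment-emergent PCSVs will be defined in the SAP".

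SAP 10.1 supplies the criteria. For CLcr (Cockcroft-Gault) and for eGFR (MDRD), the PCSV column holds the same five bands. The lower three are "<15 (end stage renal disease) ≥15 - <30 (severe decrease in GFR) ≥30 - < 60 (moderate decrease in GFR" and the upper two are "≥60 - <90 (mild decrease in GFR) ≥ 90 (normal GFR". Neither entry states a baseline condition, a direction of change, or that the bands are descriptive.

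SAP 5.8.2 says what is tabulated: "The number (n) and percentage (%) of subjects with treatment-emergent PCSVs". This is done for all SAF patients and again for the "subgroup of SAF patients who did not meet the PCSV criterion at baseline (normal or missing". SAP 6.1.2 adds one rule: "Patients who had post-baseline PCSV, but missing baseline value will be regarded as having treatment emergent PCSV".

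**The concern.** A PCSV criterion should divide results into those that deserve attention and those that do not. For CLcr and eGFR nothing falls on the second side, because a value that the appendix itself labels normal is in the PCSV column. SAP 5.8.2 assumes the opposite, since it describes patients who do not meet the criterion as normal or missing. A programmer applying 5.8.2 to these two entries cannot satisfy both sections.

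At stake is whether the CLcr and eGFR lines of the laboratory PCSV table mean anything. Depending on how the bands are programmed, the table either counts everybody or counts improvement alongside decline. Efficacy is not involved.

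**Working it through.** The plan states no figure for this point, so there is none to reproduce. The check is an enumeration of the rule as written.

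**Inputs.** The cut points 15, 30, 60 and 90 come from SAP 10.1. The two summaries come from SAP 5.8.2 and the missing-baseline rule from SAP 6.1.2. The SAP does not otherwise define treatment-emergent for a laboratory PCSV. I take the all-SAF summary to count any post-baseline PCSV, in line with Protocol 11.4.5.2, and the subgroup summary to restrict this to patients who did not meet the criterion at baseline.

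**Step 1: is the list exhaustive?** The bands are x < 15, 15 ≤ x < 30, 30 ≤ x < 60, 60 ≤ x < 90 and x ≥ 90. Applied to 2,501 values (0 to 250 in steps of 0.1), each value meets exactly one band. So 2,501/2,501 = 100% of values are PCSVs.

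**Step 2: what gets counted?** The baseline and post-baseline pairs below are illustrative values, not taken from the documents.

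| Baseline → post | One criterion, all SAF | One criterion, not met at baseline | Row by row, newly met band | Below 90 and worse than baseline |
|---|---|---|---|---|
| 105 → 104 | counted | no | none | no |
| 75 → 76 | counted | no | none | no |
| 85 → 95 | counted | no | ≥90 | no |
| 55 → 65 | counted | no | 60 to <90 | no |
| 95 → 85 | counted | no | 60 to <90 | 60 to <90 |
| 65 → 55 | counted | no | 30 to <60 | 30 to <60 |
| missing → 100 | counted | counted | ≥90 | no |

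*One criterion.* Every patient with a post-baseline value is counted in the all-SAF summary. The subgroup contains only patients with a missing baseline, and each of them with a post-baseline value counts under SAP 6.1.2, even at 100. Blood chemistry is scheduled at screening (Protocol Table 1), so that subgroup should be empty or nearly so.

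*Row by row.* Each patient sits in one band, so no single row reaches 100% by construction. In the not-met-at-baseline summary, however, 85 → 95 is new in the normal band and 55 → 65 is new in the mild band.

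**Step 3: is deleting the normal band enough?** No. It removes 85 → 95 and missing → 100, but 55 → 65 still newly meets the 60 to <90 band. Requiring a worse band than baseline as well leaves only the two declines, 95 → 85 and 65 → 55 (last column).

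**Illustration of size, row by row.** The documents give no GFR distribution. Assume true GFR with mean 90 to 110 and SD 15 to 20, within-person CV 5% to 12%, and no drug effect. Simulation then gives about 6% to 31% of patients changing band between two measurements. About half of those moves are upward, as expected when nothing changes on average. The defect does not depend on these percentages.

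**The case against.** The strongest reply is that these are staging bands. Each has a stage label, the Comments column cites a regulator's draft guidance on pharmacokinetics in renal impairment, and 5.8.2 plainly regards normal as outside the PCSV definition. A row printed as normal GFR would be recognised for what it is. That is a plausible account of intent, but the SAP does not say so. The ALT and AST rows are marked as a distribution analysis and list only abnormal values; the renal rows have no such mark.

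Second, the rule may never be run. The chemistry panel in Protocol 9.2.3.4 includes creatinine but neither CLcr nor eGFR, and the SAP does not state that they will be derived. The appendix also lists other tests outside the panel, such as lipase, amylase, HbA1c and CRP, and looks like a template. This stands, and the point is conditional on derivation.

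Third, many other rows (sodium, potassium, platelets) also lack a baseline condition and rely on the 5.8.2 subgroup to supply one. That is true. For those rows the subgroup works because some values do not meet the criterion. For CLcr and eGFR none do.

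Two stronger readings are tempting. A reader might infer that the rule both fires for every patient and reports improvement as a treatment-emergent safety signal. These effects belong to different readings. On the one-criterion reading, an 85 → 95 patient already met the criterion at baseline and cannot be told apart from anyone else. On the row-by-row reading, no row fires for everyone. A reader might also infer that the trial could not detect renal harm. The documents do not support that: SAP 10.1 has separate criteria for creatinine (≥150 µmol/L, and rises of ≥30% and ≥100% from baseline as a change criterion) and for blood urea nitrogen (≥17 mmol/L). SAP 5.8.2 plans change-from-baseline summaries and normal/abnormal shift tables, and entries to the lower GFR bands would remain visible row by row.

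**Conclusion.** The criteria are wrong as written. The CLcr and eGFR entries in SAP 10.1 leave no value outside the PCSV definition and contradict the meaning of normal in SAP 5.8.2. If the parameters are derived, the one-criterion count is 100% of patients with a post-baseline value in both arms, with a subgroup limited to patients missing a baseline. The row-by-row count treats moves to a better band as new PCSVs. The first result follows from the text alone. How often the second occurs depends on GFR values that the documents do not give.

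The practical weight is small: two descriptive safety parameters, in a study stopping at about 40 patients with exploratory analyses only, and with other renal measures intact.

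**What to change.** In SAP 10.1, remove the ≥90 band from the PCSV criteria for CLcr and eGFR. State that a treatment-emergent renal PCSV is a post-baseline value below 90 that lies in a worse band than baseline or, when baseline is missing, any post-baseline value below 90. This follows the at-baseline/post-baseline form that the same appendix already uses for QRS and hemoglobin, and it narrows SAP 6.1.2 for these two parameters.

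If the five bands are meant only as a descriptive classification, label them so and exclude them from the PCSV counts. In either case, state whether CLcr and eGFR will be derived at all.

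The cost is two rows of wording and a small change to the derivation, with no new data. The downside is a departure from the template for two rows. Chance moves such as 95 → 85 would also still be flagged in the mildest band. Under the illustrative assumptions above, about half of 6% to 31%, that is roughly 3% to 16% of patients, would be flagged with no drug effect, so that band should be read with this in mind.
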